### 6.1 Procedures to Be Performed before Patient Registration

The procedures listed below will be performed, and the results will be recorded in the CRF.

For each assessment item, data obtained before informed consent within the allowable time limits for each item may also be used.

If the study drug is started on Day 7 or later if the day of registration is defined as Day 0, the patient's eligibility should be assessed again on the preceding day or the start day (before dosing) of treatment with the study drug.

If 12-lead ECG measurement, vital sign measurement, and blood collection for laboratory tests etc. are scheduled on the same day, blood collection will be performed after 12-lead ECG and vital sign measurements.

- 1) Items to be collected or assessed after informed consent is obtained but before the start of the patient registration procedure
  - If informed consent for tests for mutations of the FLT3-ITD gene is obtained before obtaining informed consent for participation in the study, the date of informed consent
  - Date of informed consent for participation in the study
  - Presence or absence of mutations of the FLT3-ITD gene and FLT3-ITD assessment result
    - Mutations of the FLT3-ITD gene will be tested at Navigate BioPharma using peripheral blood or bone marrow liquid after informed consent. Patients who have not previously undergone mutation tests of the FLT3-ITD gene at any testing company may be tested for mutations of the FLT3-ITD gene at SRL, if necessary, and their eligibility for the study may be assessed without having to wait for the result of the test at Navigate BioPharma.
    - If the test result of Navigate BioPharma is found to be different from the test result of the hospital or SRL after registration based on the result of the previous FLT3-ITD mutation test performed at the testing company or SRL, the investigators will decide whether to continue treatment with the study drug or not for the concerned patient. In other words, even if the test result of Navigate BioPharma is negative, if continued treatment with the study drug may be beneficial to the patient in the opinion of the investigators, treatment with the study drug may be continued.
  - Subject identification code

- Date of birth
- Sex
- Race
- Height
- Eligibility
- Medical history and complications

Assess the presence or absence of medical history and complications, presence or absence of symptoms on the day of the first dose of the study drug (if any symptoms are present, it should be handled as a complication), findings, and the diagnosis.

Only the medical history that needs to be reported in the opinion of the investigators, will be listed.

- Information on the underlying disease (AML)
   Collect data on the date of the first diagnosis, the WHO classification, and the date of relapse.
- Prior therapy:

Collect data on the following items:

- Medications for AML: Presence or absence, drug name, stop date, best response, number of courses
- Radiation therapy for AML: Presence or absence, purpose, location, stop date, best response
- HSCT: Presence or absence, details, date of transplantation
- Others: Presence or absence, details, stop date
- Confirmation of serious adverse events (SAEs)
   Information on SAEs that occur during the period from informed consent to before the first dose of the study drug will be collected. Collection of information on nonserious AEs is not required.
- 2) Items to be collected or assessed between Day 14 and Day 0 ( day of registration) (collected or assessed on a day as close as possible to the day of registration)
  - Vital sign measurement
     Axillary body temperature, pulse rate, and systolic and diastolic blood pressure
     will be measured in the supine position after a 5-minute rest.
  - Body weight
  - ECOG PS assessment

The patient's PS will be assessed according to the criteria provided in Appendix 2.

## • 12-lead ECG (including QTcF assessment)

A 12-lead ECG will be performed in triplicate in the supine position after a 10-minute rest. The measurements will be performed at approximately 3- to 5-minute intervals.

## Laboratory tests

	Laboratory Parameter
Hematology test	Red blood cell count, mean corpuscular volume (MCV), mean corpuscular hemoglobin (MCH), mean corpuscular hemoglobin concentration (MCHC), hemoglobin, hematocrit, white blood cell count, white blood cell differential count (neutrophils, basophils, eosinophils, lymphocytes, monocytes), platelet count, and PT INR
Blood chemistry test	Total protein, albumin, total bilirubin, direct bilirubin, AST, ALT, ALP, γ GT, LDH, lipase, BUN, serum creatinine, creatine kinase, uric acid, glucose, electrolytes (K, Na, Cl, Ca, P, Mg), CRP, total cholesterol,* LDL,* HDL,* and triglyceride*
Urinalysis	Specific gravity, pH, occult blood, glucose, protein, bilirubin, and ketone bodies

\* These parameters will be measured only at screening and at the time of discontinuation (no dietary restrictions).

## Assessment of bone marrow findings

Assessment will be made based on the bone marrow findings and peripheral blood results (neutrophil count, platelet count, and presence or absence of blasts) in accordance with "7.1 Definition of Efficacy Endpoints." Even if a bone marrow test is not performed within 14 days (Day 14) before registration (day of registration is regarded as Day 0), if consent of the medical monitor etc. is obtained, the concerned data may be used for assessment of bone marrow findings.

• Chest X-ray (Posterior or lateral radiographs will be taken, as necessary.)

A urine or serum pregnancy test will be performed in female patients.

#### Pregnancy test

A pregnancy test is not necessary in women who have been amenorrheic for at least 2 years after the last menstruation and who are considered to have no childbearing potential, or women who are not of childbearing potential after

permanent surgical sterilization, etc. In this case, the information and reason will be recorded in the CRF.

A pregnancy test must be performed in women who have been amenorrheic for at least 2 years for medical reasons other than surgical sterilization (eg, medication) because they are considered to have childbearing potential.

• A MUGA scan or echocardiography (however, excluding cases of LVEF of 45%

or more based on the result of the test performed within 1 month after the screening test)

- 3) Items to be collected or assessed between Day 120 and Day 0 ( day of registration)
  - HIV antibody

## 6.2 Procedures during the Study Conduct Phase

The procedures listed below will be performed, and the results will be recorded in the CRF.

The details of the procedures are the same as those described in "6.1 Procedures to Be Performed before Patient Registration."

If 12-lead ECG measurement, vital sign measurement, and blood collection for laboratory tests etc. are scheduled on the same day, blood collection will be performed after 12-lead ECG and vital sign measurements.

- 1) Confirmation of the status of administration of the study drug
  - Presence or absence of administration
  - Dates of doses administered
  - Timing of dosing
  - Amount of dose administered (mg/day)
  - Presence or absence of interruption and dose reduction (if present, the details and reason for it)

### 2) Vital sign measurement

Day 1	Pre dose
* Day of the first dose	
of the study drug	
Day 2	Pre dose
Day 8 (±1 day)	Pre dose
Day 15 (±1 day)	Pre dose
Day 1 (±3 days)	Pre dose
Day 15 (±1 day)	Pre dose
Day 1 (±3 days)	Pre dose
	* Day of the first dose of the study drug  Day 2  Day 8 (±1 day)  Day 15 (±1 day)  Day 1 (±3 days)  Day 15 (±1 day)

## 3) Body weight

Cycle 1	Day 1	Pre dose
	* Day of the first dose	
	of the study drug	
Cycle 2 and thereafter	Day 1 (±3 days)	Pre dose

### 4) ECOG PS assessment

Cycle 1	Day 1	Pre dose
	* Day of the first dose	
	of the study drug	
Cycle 2 and thereafter	Day 1 (±3 days)	Pre dose

### 5) 12-lead ECG

A 12-lead ECG will be performed in triplicate (triplicate ECG) in the supine position after a 10-minute rest. The measurements will be performed at approximately 3- to 5-minute intervals. For the details, refer to "9.10.1 Measurement Method." It should be noted that the measurement time points are different if the dose of quizartinib is increased or not increased on Day 16 of Cycle 1, as shown below.

Cycle 1	Day 1	Pre dose
	* Day of the first dose	2 hours (±10 minutes) post dose
	of the study drug	4 hours (±10 minutes) post dose
		6 hours (±10 minutes) post dose
	Day 2	Pre dose (24 hours post dose on Day 1)
		2 to 4 hours post dose
	Day 8 (±1 day)	Pre dose
		2 to 4 hours post dose
	Day 15 (±1 day)	Pre dose
		2 hours (±10 minutes) post dose
		4 hours (±10 minutes) post dose
		6 hours (±10 minutes) post dose
Cycle 2	Day 1 (±3 days)	
	If the dose of quizartinib is increased	Pre dose
		2 hours (±10 minutes) post dose
	on Day 16 of Cycle 1	4 hours (±10 minutes) post dose
	on Buy 10 of Cycle 1	6 hours (±10 minutes) post dose
	If the dose of	
	quizartinib is not	Pre dose
	increased on Day 16 of	2 to 4 hours post dose
	Cycle 1	
Cycle 3	Day 1 ( $\pm 3$ days)	Pre dose
		2 to 4 hours post dose
Cycle 4 and thereafter	Day 1 (±3 days)	Pre dose

A 12 lead ECG will be performed at least once weekly for 2 weeks after increasing the dose of quizartinib to carefully confirm the QTcF interval.

### 6) Laboratory tests

Day 1	Pre dose
* Day of the first dose	
of the study drug	
Day 2	Pre dose
Day 8 (±1 day)	Pre dose
Day 15 (±1 day)	Pre dose
Day 1 (±3 days)	Pre dose
Day 15 (±1 day)	Pre dose
Day 1 (±3 days)	Pre dose
	* Day of the first dose of the study drug Day 2 Day 8 (±1 day) Day 15 (±1 day) Day 1 (±3 days) Day 15 (±1 day)

## 7) Assessment of bone marrow findings

Assessment will be made based on the bone marrow findings and peripheral blood results (neutrophil count, platelet count, and presence or absence of blasts) in accordance with "7.1 Definition of Efficacy Endpoints."

It is desirable to obtain bone marrow specimens by bone marrow aspiration and biopsy. If the investigator or subinvestigator considers that the antitumor effect of quizartinib can be assessed adequately using specimens obtained by bone marrow aspiration alone, bone marrow biopsy may be omitted.

Cycle 2	Day 1	On the specified day (±3 days)
Cycle 3	Day 1	On the specified day (±3 days)
Cycle 4 and thereafter	Day 1	On the specified day (±3 days)

After achievement of CR, CRi, or CRp, the antitumor effect will be assessed every 3 cycles until the appearance of leukemic blasts in the peripheral blood. Assessment will be performed at other time points if necessary.

## 8) Confirmation of concomitant drugs and therapies, and transfusion

### Concomitant drugs and therapies

The following information on concomitant drugs and therapies other than the study drug, which are used during the period from the day of the first dose of the study drug to the day of post-treatment observation will be confirmed. As for concomitant drugs or therapies that are newly started after the day following the last dose of the study drug, those used only for the treatment of AEs will be confirmed.

- Name of drug (therapy), dose, unit, mode of administration, frequency
- Start and stop dates of drug (therapy)
- Reason for use (application)

The following items do not have to be recorded in the CRF unless a relationship of them with the AEs occurring during study participation cannot be ruled out:

- Antiseptic solutions
- Heparin for heparin lock flush
- Test or procedural agents used for tests including bone marrow aspiration or biopsy

#### Transfusion

The following information on transfusion that is introduced during the period from the day of the first dose of the study drug to the day of post-treatment

observation will be confirmed. As for transfusion that is newly started after the day following the last dose of the study drug, the one used only for the treatment of AEs will be confirmed.

- Type of blood products (whole blood, red blood cells, plasma, platelets, others)
- Start date, end date, amount of use (unit)
- Reason for use
- 9) Monitoring of AEs
- 10) Collection of specimens for pharmacokinetic assessment and the biomarker study Refer to "6.8 Pharmacokinetics," "6.9 FLT3-ITD Mutation Test," and "6.10 Biomarker Study."

### 6.3 Procedures When Treatment with the Study Drug Is Discontinued

The procedures listed below will be performed on the day when the investigators decide discontinuation of treatment with the study drug (within 3 to +7 days).

The details of the procedures are the same as those described in "6.1 Procedures to Be Performed before Patient Registration" and "6.2 Procedures during the Study Conduct Phase."

- Date of discontinuation of treatment with the study drug and reason for discontinuation
- Vital sign measurement
- Body weight
- ECOG PS assessment
- 12-lead ECG
- Laboratory tests
- Assessment of bone marrow findings (It is desirable to obtain bone marrow specimens by bone marrow aspiration and biopsy. If the investigator or subinvestigator considers that the antitumor effect of quizartinib can be assessed adequately using specimens obtained by bone marrow aspiration alone, bone marrow biopsy may be omitted.)
- Confirmation of concomitant drugs and therapies, and transfusion
- Monitoring of AEs
- Confirmation of the status of administration of quizartinib

## 6.4 Procedures during the Post-treatment Observation Period

The procedures listed below will be performed at day 30 (+15 days) when the day of the last dose of the study drug is set day 0. The post-treatment observation will be performed before the start of post treatment, if it is initiated.

The day when all the procedures have been completed is defined as the day of completion of the post-treatment observation period.

If any AEs have not resolved by the day of completion of the post-treatment observation period, follow-up should be continued as far as possible until the AE is resolved or reduced.

The details of the procedures are the same as those described in "6.1 Procedures to Be Performed before Patient Registration" and "6.2 Procedures during the Study Conduct Phase."

- Vital sign measurement
- Body weight
- ECOG PS assessment
- Laboratory tests
- Confirmation of survival (the last date of confirming survival) or death (the date of death)
- Confirmation of concomitant drugs and therapies, and transfusion
- Monitoring of AEs
- Post treatment for AML after discontinuation of treatment with quizartinib
- Presence or absence of relapsed AML, and if present, the date of relapse

#### 6.5 Post Treatment

Treatment used for AML after the day of the last dose of the study drug (eg, HSCT, chemotherapy, immunotherapy, radiation therapy, and others) is defined as "post treatment."

Post treatment should not be started before the day of completion of the post-treatment observation period as far as possible. If post treatment is started by necessity before completion of the post-treatment observation period, the name and start date of the post treatment will be recorded in the CRF.

## 6.6 Follow-up

The following information will be confirmed every 3 months after assessment during the post-treatment observation period (confirmation by phone is allowed).

- Investigation of survival status
- Post treatment for AML after discontinuation of treatment with quizartinib
- Presence or absence of relapsed AML, and if present, the date of relapse

### 6.7 Definition of the Study Period

The study period for each patient is from the time of informed consent to the end of the follow-up assessment.

#### 6.8 Pharmacokinetics

measurements.

A total of 2 mL of blood will be drawn, well mixed by inverting the tube, and centrifuged (≥ 15°C, 1500 g, 10 minutes) within 20 minutes after blood collection. The obtained plasma will be stored frozen between 90°C and 70°C. The specimens in a frozen state will be submitted to the agency contracted by the sponsor to collect the specimens. Details including the handling of specimens will be specified in separate procedures. The date and time of blood collection will be recorded in the CRF. If 12-lead ECG measurement, vital sign measurement, and blood collection are scheduled at the same time, blood collection will be performed after 12-lead ECG and vital sign

Treatment Cycle Treatment Day Blood Collection Point (Acceptable Limit) Cycle 1 Day 1 Pre dose (60 minutes) 1 hour (±30 minutes) post dose 2 hours (±30 minutes) post dose 4 hours (±30 minutes) post dose 6 hours (±30 minutes) post dose 24 hours post dose (within 3 hours pre dose on Day 2 of Cycle 1) Day 8 (±1 day) Pre dose ( 60 minutes) 2 to 4 hours post dose Day 15 (±1 day) Pre dose (60 minutes) 1 hour (±30 minutes) post dose 2 hours (±30 minutes) post dose 4 hours (±30 minutes) post dose 6 hours (±30 minutes) post dose 24 hours post dose (within 3 hours pre dose on Day 16 of Cycle 1) Cycle 2 Day 1 (±3 days) Pre dose (60 minutes) 1 hour (±30 minutes) post dose If the dose of quizartinib 2 hours (±30 minutes) post dose is increased on Day 16 of 4 hours ( $\pm 30$  minutes) post dose Cycle 1 6 hours (±30 minutes) post dose 24 hours post dose (within 3 hours pre dose on Day 2 of Cycle 2) If the dose of quizartinib Pre dose (60 minutes) is not increased on Day 2 to 4 hours post dose 16 of Cycle 1 Cycle 3 Day 1 ( $\pm 3$  days) Pre dose (60 minutes)

Table 6.8-1 Blood Collection Points for Pharmacokinetic Assessment

#### 6.9 FLT3-ITD Mutation Test

To investigate the presence or absence of mutations of the FLT3-ITD gene, 2 mL of bone marrow liquid or 4 mL of peripheral blood (1 mL of bone marrow liquid or 2 mL of peripheral blood if the measurement is not performed at SRL) will be collected after obtainment of informed consent, but before registration, and the specimen will immediately be submitted to the specimen collection agency contracted by the sponsor under the designated temperature conditions.

2 to 4 hours post dose

#### 6.10 Biomarker Study

# 6.10.1 Plasma Inhibitory Activity of Quizartinib on Phosphorylated FLT3 and c-Kit Proteins

A total of 2 mL of blood will be drawn, well mixed by inverting the tube, and centrifuged (≥ 15°C, 1500 g, 10 minutes) within 20 minutes after blood collection. The obtained plasma will be stored frozen between 90°C and 70°C. The specimens in a frozen state will be submitted to the agency contracted by the sponsor to collect the specimens. Details including the handling of specimens will be specified in separate procedures.

The date and time of blood collection will be recorded in the CRF.

If 12-lead ECG measurement, vital sign measurement, and blood collection are scheduled at the same time, blood collection will be performed after 12-lead ECG and vital sign measurements.

Table 6.10-1 Blood Collection Points for Plasma Inhibitory Activity

Treatment Cycle	Treatment Day	Blood Collection Point (Acceptable Limit)
Cycle 1	Day 1	Pre dose ( 60 minutes) 2 hours (±30 minutes) post dose
		4 hours (±30 minutes) post dose 6 hours (±30 minutes) post dose
	Day 8 (±1 day)	Pre dose ( 60 minutes)
	Day 15 (±1 day)	Pre dose ( 60 minutes)
Cycle 2	Day 1 (±3 days)	Pre dose ( 60 minutes)

#### 7. EFFICACY ASSESSMENTS

The antitumor effect of quizartinib will be assessed based on bone marrow findings and neutrophil and platelet counts in the peripheral blood, as specified in "7.1 Definition of Efficacy Endpoints."

# 7.1 Definition of Efficacy Endpoints

The efficacy endpoints are defined in Table 7.1-1.

Table 7.1-1 Definition of Efficacy Endpoints

Complete remission (CR)	For patients to be classified as CR, they must achieve a morphologic leukemia free state, must have less than 5% blasts in the bone marrow (no Auer rods), a neutrophil count of 1000/mm³ or more, and a platelet count of 100 000/mm³ or more, must be independent of red blood cell (RBC) and platelet transfusions (defined as 4 weeks without RBC transfusion and 1 week without platelet transfusion), and may not have extramedullary leukemia.
CR with incomplete hematological recovery (CRi)	For patients to be classified as CRi, they must fulfill all the criteria for CR, except for incomplete hematological recovery with residual neutropenia of less than 1000/mm  . Platelet recovery status and RBC and platelet transfusion independence are not required.
CR with incomplete platelet recovery (CRp)	For patients to be classified as CRp, they must fulfill all the criteria for CR, except for incomplete platelet recovery (< 100 000/mm  ).
Partial remission (PR)	For patients to be classified as PR, they must have bone marrow regenerating normal hematopoietic cells, no or minimal residual blast cells in the peripheral blood, a decrease of at least 50% in the percentage of blasts in the bone marrow aspirate, and total marrow blasts between 5% and 25% inclusive. Whether the neutrophil count or platelet count has recovered or not, or whether erythrocyte or platelet transfusion has been performed or not, will not be taken into consideration.
No response (NR)	NR is defined as a condition not reaching any of CR, CRi, CRp, or PR.
Unknown	No assessment is made after baseline.
Composite CR rate (CRc rate)	Composite CR rate (CRc rate) is defined as the proportion of patients whose best response is CR, CRi, or CRp.
Response rate	Response rate is defined as the proportion of patients whose best response is CR, CRi, CRp, or PR.
Relapse	Relapse after CR, CRi, or CRp:  Defined as the reappearance of leukemic blasts in the peripheral blood or an increase in the percentage of blasts in the bone marrow aspirate to 5% or more, or the reappearance or new appearance of extramedullary leukemia.  Relapse after PR:  Defined as the reappearance of significant numbers of blasts in the peripheral blood or an increase in the percentage of blasts in the bone marrow aspirate to more than 25%, or the reappearance or new appearance of extramedullary leukemia.

# 7.2 Best Response

Best response is defined as the best measured response over all response assessments (CR, CRp, CRi, PR, NR, or Unknown) at all time points after the first dose of the study drug. The best response is presented as CR, CRp, CRi, PR, NR, or Unknown in descending order of efficacy.

# 7.3 Primary Efficacy Endpoint

The primary efficacy endpoint of this study is the CRc rate. The CRc rate is defined as

the proportion of patients whose best response is CR, CRp, or CRi.

# 7.4 Secondary Efficacy Endpoints

The secondary efficacy endpoints of this study are as follows.

- Best response
- Response rate
- Overall survival (time from registration to death)
- Event-free survival (time from registration to progression, relapse, or death, whichever occurs first)
- Leukemia-free survival (time from first achievement of CRc to relapse or death, whichever occurs first)
- Transplantation rate (proportion of patients who start HSCT immediately after the end of treatment with the study drug without receiving other treatment for AML)

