### **5.2.4.2** Regimen

Quizartinib will be orally administered once daily every morning. Treatment with quizartinib will be administered in 28-day cycles and continued until "5.7.1 Discontinuation Criteria for Treatment with the Study Drug" are met. The first dose of the study drug will be started, in principle, within 7 days of registration. If treatment with the study drug is started more than 7 days after registration, it should be confirmed again that the patient meets the eligibility criteria before the start of the first dose of the study drug.

If a patient vomits after taking a dose of the study drug, a replacement dose may not be given on the same day.

A patient who did not take the study drug at the usual hour of dosing (eg, forgot to take the dose) will be allowed to take the missed dose within 10 hours after the usual hour of dosing (for example, if the patient usually takes the drug at 7:00 or 8:00, he/she may take it by 18:00). In this case, the next dose of the study drug on the following day should be taken at least 12 hours after the time when the last dose was taken. If the patient does not take the missed dose by 10 hours after the usual hour of dosing, he/she should not take the study drug on that day and resume taking the drug on the following day. The patient may not take two doses at once on the day when the drug is resumed.

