# 11.2 Analysis Sets

The sponsor will finalize the population flag of individual patients for each analysis set after CRF lock. Patients with major Good Clinical Practice (GCP) violations (eg, a violation of the informed consent procedure, a major violation of study procedures) will be excluded from all analysis sets.

- All enrolled patients will include all patients who have signed the ICF.
- All registered patients will include all patients who have signed the ICF and are assessed as eligible for the study.
- The safety analysis set will include all patients who have signed the ICF and received at least one dose of the study drug.
- The efficacy analysis set will include patients who have signed the ICF (including consent for measurement of FLT3-ITD mutations), have a positive result of the FLT3-ITD mutation test performed at Navigate BioPharma, and have received at least one dose of the study drug.
- The pharmacokinetic analysis set will include patients who have signed the ICF and received at least one dose of the study drug, and whose plasma drug concentration data obtained are available for at least one time point after the start of treatment with the study drug.
- The biomarker analysis set will include patients who have signed the ICF and received at least one dose of the study drug, and whose biomarker data shown in Section 6.10 are available for at least one time point after the start of treatment with the study drug.

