#### 11.3 Statistical Analyses

# 11.3.1 Efficacy Analyses

Efficacy analyses will be performed in the efficacy analysis set.

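### OS and EFS are timed from registration but analysed only in patients who later received a dose, which biases both upward by a modest amount

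*Combined protocol and SAP*

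**What the plan says.** Section 7.4 lists "Overall survival (time from registration to death" and "Event-free survival (time from registration to progression, relapse, or death, whichever occurs first" among the secondary efficacy endpoints. The third time-to-event endpoint has a different origin: "Leukemia-free survival (time from first achievement of CRc to relapse or death, whichever occurs first".

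Section 11.3.1 fixes the population: "Efficacy analyses will be performed in the efficacy analysis set". Under Section 11.2, members of that set must have given consent, including for the mutation test, and must "have a positive result of the FLT3-ITD mutation test performed at Navigate BioPharma, and have received at least one dose of the study drug". Section 11.2 also defines a wider set, "All registered patients will include all patients who have signed the ICF and are assessed as eligible for the study", but no survival analysis uses it.

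On timing, Section 5.1.2 bars dispensing the drug before registration. Section 5.2.4.2 says "The first dose of the study drug will be started, in principle, within 7 days of registration". It allows a later start once eligibility has been confirmed again, and sets no outer limit.

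Section 11.3.1.2 plans Kaplan-Meier curves and a median with a 95% CI. The text supplied has no delayed entry, no landmark, and no sensitivity analysis with another origin or population.

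**The concern.** The clock starts at registration, but a patient joins the analysis only by being dosed, which comes later. A patient who dies between the two is counted nowhere in OS or EFS. A patient who survives to be dosed keeps the waiting time as follow-up. This is immortal time: an interval in which, by construction, no analysed patient can have died.

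For EFS the strict guarantee also covers death only. In practice progression is unlikely to be recorded in the gap either, because Table 6-1 schedules marrow assessment at screening and next on Day 1 of Cycle 2, with extra assessments only if the investigators think them necessary.

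The trial has one arm, so its OS and EFS medians have no internal comparator. Anyone who puts them in context will use outside figures such as the overseas medians in Section 1.2.1.2.2. Those passages do not state the overseas time origin, so it cannot be assumed that the bias cancels.

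**Working it through.** **Plan's own figures.** The plan gives no planning figure for OS or EFS. Its CRc operating characteristics (Section 11.5) reproduce by exact binomial calculation: probability of declaring efficacy 0.048 at a true rate of 23.5% and 0.814 at 42%, with an expected 33.0 patients at 42%. None of these uses a survival time, so they do not depend on the origin.

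**Inputs**
- Gap g from registration to first dose: in principle 0 to 7 days (Section 5.2.4.2). The actual distribution is not given. I show 1, 3 and 7 days, and 14 days as a late start.
- Median OS for scale: 24.0 weeks and 25.3 weeks in the FLT3-ITD positive subsets of the two cohorts of Study AC220-002 (Section 1.2.1.2.2), and 8.6 weeks at the low end of the range in Section 1.2.1.3.
- Median EFS: not given. I assume 6 to 12 weeks.

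**Comparison A: the same dosed patients, timed from first dose.** Time from registration equals g plus time from first dose for each patient. With a common gap, the median moves by exactly g whatever the survival distribution. The relative shift is g/M, with M the median from first dose:
- M = 24.0 weeks: 1 day, 0.14/24.0 = 0.6%; 3 days, 0.43/24.0 = 1.8%; 7 days, 1.0/24.0 = 4.2%; 14 days, 2.0/24.0 = 8.3%.
- M = 25.3 weeks, 7 days: 1.0/25.3 = 4.0%.
- M = 8.6 weeks, 7 days: 1.0/8.6 = 11.6%.
- EFS, assumed M of 6 to 12 weeks, 7 days: 1.0/6 = 16.7% down to 1.0/12 = 8.3%.

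**Comparison B: all registered patients, timed from registration.** Let S be survival from registration, and assume that only death prevents dosing. The planned median solves S(t) = 0.5 × S(g). Since S(g) cannot exceed 1, this t is never earlier than the true median, so the direction is fixed. For a Weibull distribution with shape k and all-registered median M, the planned median is (M^k + g^k)^(1/k), and the probability of death before dosing is 1 − exp(−ln 2 × (g/M)^k). With M = 24 weeks and g = 1 week:

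| Shape k | Death before dose | Planned median | Excess over all registered | Dosed patients, from first dose |
|---|---|---|---|---|
| 0.7 (early hazard high) | 7.2% | 27.8 wk | 3.8 wk | 26.8 wk |
| 1 (constant hazard) | 2.8% | 25.0 wk | 1.0 wk | 24.0 wk |
| 1.5 (early hazard low) | 0.6% | 24.1 wk | 0.14 wk | 23.1 wk |

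At 3 days the excess is 2.07, 0.43 and 0.04 weeks. Under constant hazard, the deaths excluded per 41 dosed patients are 41 × 0.0123/0.9877 = 0.5 at 3 days and 41 × 0.0285/0.9715 = 1.2 at 7 days.

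The last column shows that timing from first dose makes origin and population agree. It does not recover the all-registered median unless the hazard is constant.

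**The case against.** The best case against acting is that the effect is small and no decision rests on it. OS and EFS are descriptive, with no test or threshold. Assuming exponential survival, 30 deaths and a 24-week median, the 95% CI is about 24 × exp(±1.96/√30), or 17 to 34 weeks. A shift of 0.4 to 1 week is minor beside that. The gap is unknown, and 7 days is the in-principle maximum rather than a typical value. Eligibility requires ECOG 0 to 2, adequate organ function and no uncontrolled infection, so hazard in the first days may be low. All of this stands, and it limits the weight of the point. It does not remove the mismatch: the bias keeps its direction, while sampling error does not.

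Three stronger readings are tempting, and the documents do not support them.
- *Every patient carries guaranteed event-free time.* Dosing on the day of registration is not forbidden and gives a zero gap. For EFS, only freedom from death is strictly guaranteed.
- *Patients who deteriorate before dosing are removed.* The set excludes for lack of a dose, not for deterioration. A patient who worsens but is still dosed stays in. The eligibility re-check after a delay could keep some sicker patients from being dosed, but the plan does not let one say how many.
- *The median always shifts by about the gap.* That holds against timing from first dose, or under constant hazard. Against all registered patients, the 7-day shift runs from 0.14 to 3.8 weeks across the shapes above.

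Section 11.6 also defers detailed methods to a separate SAP, and no separate SAP text appears in what was supplied. A sensitivity analysis or a count of undosed patients may be specified there. The origin and the population, however, are both set in the protocol.

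**Conclusion.** The point holds as a modest, upward bias in two descriptive secondary endpoints. Against timing from first dose, each patient's OS and EFS are longer by that patient's own gap: 0 to 7 days under the in-principle rule, or 0% to 4% of a 24-week median OS. The excess is larger if starts after 7 days occur, and relatively larger for EFS (8% to 17% at 7 days, on an assumed median of 6 to 12 weeks). Against all registered patients the direction is the same, but the size depends on an early hazard that the documents do not describe.

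A reader might infer that the trial's conclusion is at risk. It is not: the CRc endpoint, the stage rules, alpha and power do not use the origin, and leukemia-free survival starts at a remission that can only follow dosing. The figures assume a common gap and, for comparison B, that only death prevents dosing. This is a cheap improvement, not a design fault.

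**What to change.** In Section 7.4 and the SAP, define OS and EFS in the efficacy analysis set as time from the date of first dose. Report alongside them the number of patients registered but not dosed, with reasons, and the distribution of the interval from registration to first dose.

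The cost is a one-line change to each definition. The treatment start date is already recorded in the CRF (Section 5.5). The reported medians become a few days shorter, and they describe survival after starting treatment, not survival from registration.

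Keeping the registration origin, in all registered patients with a positive central FLT3-ITD result, is a secondary option and is not free. Post-treatment observation and follow-up (Sections 6.4 and 6.6) are anchored to the last dose, so no survival collection is planned for patients never dosed. That option works only if such collection is added.
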